## 11.7 Insulin Growth Factors (IGFs)

These tests will be performed by ARUP Laboratories at the University of Utah. ARUP is a national full-service reference laboratory that serves more than 50 academic medical centers, as well as many community hospitals, commercial laboratories, military and government facilities, and pharmaceutical firms. One 1mL aliquot will be sent by the coordinating center to ARUP Laboratories for measurement of the following IGFs. A second 1mL aliquot will be held for IGF evaluation in the case extra serum is needed.

11.7.1 IGF-1 will be measured as circulating markers of BC risk. The assay will be conducted using Chemiluminescent Immunoassay. The sensitivity of the assay is 5.1 ng/mL. The expected postmenopausal range is 58-318ng/mL. The expected premenopausal range is 89-397ng/mL.

11.7.2 IGFBP3 will be measured as circulating markers of BC risk. The assay will be conducted using Chemiluminescent Immunoassay. The sensitivity of the assay is 38.2 ng/mL. The expected postmenopausal range is 2514-6014 ng/mL. The expected premenopausal range is 2926-5858ng/mL.

## 11.8 Bone metabolism marker assays

Blood and urine will be collected at baseline and at the one-year and two-year visits at the local site and sent directly to ARUP Laboratories per instructions in Sections 11.3 and 11.4 (see address in Section 11.7).

11.8.1 *Serum bone-specific alkaline phosphatase (BSAP)* will be measured as a marker of bone formation. It is an isoenzyme of alkaline phosphatase localized on the cell membrane of osteoblasts. The assay employs a solid phase two-site immunoradiometric assay (IRMA). The sensitivity of the assay is 2.0 µg/L. The expected postmenopausal range is 7.0-22.4 µg/L. The expected premenopausal range is 4.5-16.9 µg/L.

11.8.2 *Urine N-telopeptide crosslinks (NTX)* will be measured as a marker of bone resorption. Type I collagen comprises 90% of organic bone. It is a helical protein that is cross-linked at the N-terminal and C-terminal ends. These crosslinks are released during bone remodeling by osteoclasts. They are then found in the urine as a stable end-product of bone metabolism. The procedure is chemiluminescent immunoassay. Final values are reported as bone collagen equivalents (BCE) in nM/L corrected for creatinine clearance in mM/L. The expected range in postmenopausal women is 26-124 nM BCE/mM creatinine. The expected premenopausal range is 17-94 nM BCE/mM creatinine.

#### 11.9 **Lipid assays**

Blood will be drawn into a red-top tube at baseline before the first dose of treatment and then annually (Day 365 and 730), each time after an 8-hour fast. This blood sample will be sent directly to the CLIA-approved chemistry lab for determination of *triglycerides (TG)*, *total cholesterol (TC)*, *high-density lipoprotein (HDL)*, and *low-density lipoprotein (LDL)*. Results will be faxed back to the coordinating site.

Although lipid profile abnormalities alone will not be considered an indication for stopping study protocol therapy, lipids will be monitored and treated according to NCEP ATP guidelines (<http://www.nhlbi.nih.gov/guidelines/cholesterol/atglance.pdf>).

#### 11.10 **Clotting assays**

Blood will be collected into at baseline and at the one-year and two-year visits at the local site and sent directly to the CLIA-approved hematology laboratory at each local site for determination of anti-thrombin III per institutional protocol. Results will be entered into the study EDC website.

#### 11.11 **Pharmacokinetic and pharmacogenetic measures**

Plasma will be processed from each scheduled blood draw and will be stored for the measurement of tamoxifen levels and levels of the tamoxifen metabolites, N-desmethyl-tamoxifen (also known as endoxifen) and 4-OH-tamoxifen, at the time of trial completion.

Blood will be also processed for DNA to allow for analyses of P450 SNPs including CYP2D6 polymorphisms after trial completion and unblinding. Stored DNA may also be used to explore DNA adduct formation during the course of tamoxifen treatment.

The SNP studies will be performed using commercial assays developed by Roche Laboratories.

#### 11.12 **Specimen storage**

Unused biological materials will not be discarded, and will be stored for possible future research purposes in the UAB Institute for Cancer Outcomes and Survivorship laboratory. IRB approval will be sought prior to their use for purposes other than those specifically outlined in this protocol. In addition, ancillary studies must be approved by the Consortium for Pediatric Interventional Research (CPIR) and all other participating institutions.

### 11.13 Questionnaire data

Self-reported and CRA/CRN administered questionnaires will be used to obtain baseline data on demographics, family history, reproductive history, and other BC risk factor exposure, as well as to assess patient reported symptoms during the course of the study. The self-reported questionnaires (**Demographic and Breast Cancer Risk Factors Form, QOL Form, Family History Form and the Symptom Log**) are considered source documents themselves and are not required to be accompanied by a source document, because of the design of the study. Utilizing the study EDC website, these questionnaires will be entered electronically, in compliance with FDA Regulation 21 CFR Part 11.

#### Patient demographics and baseline BC risk factors:

Standardized questionnaires will be used to obtain the following prior to study entry:

- demographic reproductive history, and BC risk factors information (**Demographics and Breast Cancer Risk Factors Form**),
- health and physical (**H&P Form**)
- family history (**COH DPS Family History Form**),

The salient domains captured by these questionnaires include date of birth, gender, race/ethnicity, socioeconomic status, and both familial and environmental BC risk factors. This questionnaire will be administered at the time of initial registration.

#### Clinical data regarding prior Cancer diagnosis and treatment:

The following information will be obtained from medical records using a standardized data abstraction form (the **Primary Cancer Treatment History Form**): date of diagnosis, stage of disease (with or without “b” symptoms), histological subtype, data elements regarding chemotherapy including dates, protocols/regimens, cumulative doses of therapeutic agents per square meter; and data regarding radiation therapy including dates, total lifetime dose, field, fractions, dose per fraction. A copy of institutional radiation oncology summary report will be obtained whenever possible.

#### Patient reported symptoms and adherence to the chemopreventive agent:

The National Surgical Breast and Bowel Project (NSABP) developed a standardized quality of life (QOL) questionnaire to assess patient reported symptoms in response to hormonal interventions, which they used in the NSABP P-1 and P-2 breast cancer prevention trials (**NSABP QOL questionnaire**). The most recent version of this questionnaire, which was used in the NSABP P-2 trial [101], will be used. The salient domains captured by this questionnaire include both physical and mental well-being. In addition, a **Symptom Log** including the **HEAL hormone-related symptoms instrument** will be used [102]. This questionnaire captures general symptoms along with specific hormone-related symptoms along the following scales: vasomotor, vaginal, incontinence, cognitive/mood, and weight gain/appearance. Both questionnaires will be administered at baseline and during the two-year treatment period according to the study calendar. Pill counts will also be used to determine adherence to the prescribed intervention using the **Adherence Tracking Form**.

Patients who report intolerable hot flashes may be managed with any of the following interventions (please refer to the **Treatment and Follow-up SOP** for recommended algorithm):

- Vitamin E 800 IU po daily
- Effexor (venlafaxine) XL 37.5-75 mg po daily

- Neurontin (gabapentin) 300mg po TID
- Lyrica (pregabalin) 75mg po BID

Patients who report vaginal atrophic symptoms may be managed with any of the following interventions (please refer to the [Treatment and Follow-up SOP](#) for recommended algorithm):

- Replens
- Astroglide
- Vagifem
- Estring

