### 7.2 **Concomitant and Repeat Therapy**

No concomitant therapy is allowed with the exception of continued medications for chronic illnesses that are not excluded in Section 5.0, and necessary medications for unrelated acute illnesses that may occur during the study (cold, flu, infection, etc.). Any such medications must be recorded. Ingestion of certain natural products should also be monitored while on trial, as outlined in Section 11.14.

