#### 11.14 Natural products known to modulate estrogens

The following herbal supplements have been associated with hormonal activity. The primary endpoint, mammographic density, is positively correlated with estrogen levels. Therefore, subjects will be asked to avoid these items before during the treatment period. Any use will be recorded along with medication changes during the course of the trial.

- |                                  |                                       |
|----------------------------------|---------------------------------------|
| • Alfalfa                        | • Isoflavones                         |
| • Bee Pollen                     | • Kava                                |
| • Black Cohosh                   | • Kudzu                               |
| • Blue Cohosh                    | • Licorice                            |
| • Cats Claw                      | • Lignans                             |
| • Chasteberry                    | • Passionflower                       |
| • Chysin                         | • Propolis                            |
| • Coumestans                     | • Red clover or other clover extracts |
| • Cramp Bark                     | • Sarsaparilla                        |
| • Dong Quai, or Chinese Angelica | • Saw palmetto                        |
| • DHEA                           | • Shepherds purse                     |
| • Evening Primrose               | • Soy extracts                        |
| • Feverfew                       | • St. Johns Wort                      |
| • Flaxseed                       | • Valeriana                           |
| • Ginseng                        | • Wild yam                            |
| • Hops                           |                                       |

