**Objective safety measures:**

**Adverse events.** The number of grade 2-4 toxicities observed will be tabulated by treatment arm. Differences by treatment arm will be evaluated using Fisher exact tests.

**Biomarkers.** Total cholesterol, low and high density lipoprotein, triglycerides, anti-thrombin III enzymatic assay (for clotting propensity), and serum bone-specific alkaline phosphatase (BSAP, for bone formation) and urine N-telopeptides (NTX, for bone resorption) measurements will be treated as continuous variables. Transformed to normality as appropriate, the linear mixed effects model will be applied, using the unstructured mean model using and linear in time model, to assess the effects of low dose tamoxifen on these measurements over time.

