**Subjective safety and tolerability measures:**

**Treatment adherence.** Compliance will be measured by pill counts performed every 3 months. The number of pills taken out of the total prescribed in a 3-month period will be modeled as a random effects binomial regression model [105]. The binomial rates from 8 time points (month 3 to 24) will be modeled as unstructured mean model with 7 indicator variables as well as polynomial models over time. The random-intercept and the random intercept and slope models will be considered. The significance of the time indicators or parameters by treatment interaction will be evaluated for treatment difference in compliance.

Voluntary withdrawals will be examined at the end of the study by comparing the percent of withdrawals between the treatment groups using a chi-square test or Fisher's exact test.

**Patient reported symptoms.** The outcomes will be scored as a 5-point Likert-type scale (0 to 4) in response to questions on how much the patients are bothered by certain symptoms. The questionnaire will be administered every six months, for a total of five time points. The responses will be treated as normally distributed, as ordinal or dichotomized variable, and we will apply the linear mixed effects model or GLMM methods to compare changes between treatment groups. Because of additional time points available, in addition to the unstructured mean model, we will also fit piecewise models with join point at 6 months, considering linear and curvilinear trajectories between 6m and 24m time points.

***Exploratory Aim 1: To examine the modifying effects of demographic, clinical, and molecular characteristics on both efficacy and safety markers.***

As the primary aim of this trial is to examine the main effects of low dose tamoxifen treatment on MBD, we will examine the modifying effects of demographic, clinical, and molecular characteristics as exploratory analysis. Even if time by treatment interaction (main treatment effect) is not significant, examining the modifying effects of covariates may reveal subgroups that respond differently to low dose tamoxifen. A three-way interaction of time by treatment by modifying variable will be included in the longitudinal model containing a two-way time by treatment group interaction. Modifying effects will be considered statistically significant if the three-way interaction is significant. The covariates of interest are described below.

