The presence/absence of gynecological symptoms (for each symptom mentioned above) will be compared between treatment groups using 2x2 tables using the Fisher exact test, stratified on CYP2D6 status. Logistic regression will be used to compare the frequency between treatments adjusted for covariates, including CYP2D6. Longitudinal analysis also will be conducted to compare the trends of the presence/absence of each of the reported gynecological symptoms over the 2 year period using the generalized linear mixed-effects model for binary outcomes.

For each liver function measure, a woman will be considered to have elevated liver function if the measurements at years 1 and/or 2 are above the upper limit of the institutional reference range and higher than her baseline pre-treatment level. These data will be coded such that those who are greater than 2-times the upper limit of the reference range will be considered to be clinically significant (grade 1 if asymptomatic and requiring no intervention; grade 2 if minimal/local/non-invasive intervention required). The frequency of women with elevated liver function measures will be compared between treatment groups using an exact test on 2x2 tables, stratified on CYP2D6. Logistic regression analysis will also be used to compare the frequency of elevated liver function between treatments, adjusted for covariates. Linear mixed-effects model for normally distributed data will also be used to compare the trends in liver function levels between the treatment groups. Procs MIXED and GLIMMIX will be used for longitudinal analysis of normally and non-normally distributed data, respectively. Poisson regression analysis will be conducted using Proc GENMOD, all in SAS 9.1 (Cary, North Carolina).

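### Treatment of hot flashes, vaginal atrophic symptoms and lipids during the trial is ignored in the longitudinal tolerability and lipid models, so arm differences there may be understated

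*Combined protocol and SAP*

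**What the plan says.** **Treatments provided.** Section 11.13 (patient reported symptoms and adherence) states: "Patients who report intolerable hot flashes may be managed with any of the following interventions", followed by four options. It continues: "Patients who report vaginal atrophic symptoms may be managed with any of the following interventions", followed by four products. Section 11.9 states that "lipids will be monitored and treated according to NCEP ATP guidelines". None of these is limited to one arm.

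**Analyses.**
- Section 12.4, Aim 2, patient reported symptoms: a 0-4 score given "in response to questions on how much the patients are bothered by certain symptoms", at five six-monthly time points, analysed by linear or generalized linear mixed models.
- Section 12.4, Exploratory Aim 2: each vasomotor or gynecological symptom, from a symptom log taken ten times, is compared by Fisher's exact test and logistic regression. A longitudinal binary model is then used to "compare the trends of the presence/absence of each of the reported gynecological symptoms over the 2 year period".
- Section 12.4, Aim 2, biomarkers (lipids at baseline, Day 365 and Day 730): "Transformed to normality as appropriate, the linear mixed effects model will be applied".

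None of these mentions rescue or lipid-lowering treatment as an outcome, covariate, intercurrent event or sensitivity analysis. The intention-to-treat statement and the as-treated analysis belong to mammographic density only, and the latter concerns adherence to study drug.

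**Recording.** Section 7.2, after listing the concomitant therapy it allows, says: "Any such medications must be recorded". Section 11.14, on natural products, says: "Any use will be recorded along with medication changes during the course of the trial".

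**The concern.** Establishing safety and tolerability is a stated objective (Section 1.2). Rescue goes to the women who are most troubled. If the drug causes the trouble, more women in the tamoxifen arm will qualify, and later scores will reflect drug plus rescue in one arm against a smaller amount of rescue in the other.

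The visit schedule sharpens this for the bother score. The symptom log is taken at Days 28 and 90, but the first post-baseline bother score comes at six months. A woman who reports intolerable hot flashes at Day 28 or Day 90 and is then treated can have every post-baseline bother score taken after rescue, so her worst period may never enter that model.

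Without the number of women starting treatment in each arm, similar scores cannot distinguish a tolerable drug from treated intolerance.

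**Working it through.** **1. The plan's own figures.** Section 12.5 gives 41% power for hot flashes at 68% v 80%. It prints no sample size beside that figure. Using the 94 per arm from its adverse-event paragraph, the exact power of a two-sided Fisher test at 0.05 is 40.6%, which agrees. For total cholesterol, 199 + 0.34 × 45 = 214.3 mg/dL also agrees, so the detectable difference is 0.34 × 45 = 15.3 mg/dL.

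The documents give no rescue uptake or rescue effect. Everything below is an assumed illustration.

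**2. Bother score, equal uptake in both arms.** Assumed shares scoring 0/1/2/3/4:
- placebo .32/.28/.20/.13/.07: mean .28 + .40 + .39 + .28 = 1.35, with 20% scoring 3-4
- tamoxifen .20/.26/.24/.18/.12: mean .26 + .48 + .54 + .48 = 1.76, with 30% scoring 3-4

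The difference is 0.41. If a share u of women scoring 3-4 takes rescue and drops d points, the observed difference is 0.41 − u × d × (0.30 − 0.20).

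| u | d | Observed difference | Reduction |
|---|---|---|---|
| 0.3 | 1 | 0.38 | 7% |
| 0.6 | 2 | 1.40 − 1.11 = 0.29 | 29% |
| 0.9 | 2 | 0.23 | 44% |

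Uptake among severe women is the same in both arms here. The shrinkage arises only because more tamoxifen women are assumed to be severe.

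**3. Hot-flash presence at a visit.** The 68% and 80% are proportions of women expected to experience hot flashes. Using them as visit-level prevalence is a further assumption. If rescue clears the symptom in shares sP and sT of symptomatic women, prevalence becomes 0.68(1 − sP) and 0.80(1 − sT). Power is for Fisher's test at one visit, 94 per arm.

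| sT | sP | Placebo | Tamoxifen | Difference (points) | Risk ratio | Power |
|---|---|---|---|---|---|---|
| 0 | 0 | 68.0% | 80.0% | 12.0 | 1.18 | 41% |
| 10% | 10% | 61.2% | 72.0% | 10.8 | 1.18 | 30% |
| 20% | 20% | 54.4% | 64.0% | 9.6 | 1.18 | 22% |
| 30% | 30% | 47.6% | 56.0% | 8.4 | 1.18 | 17% |
| 10% | 5% | 64.6% | 72.0% | 7.4 | 1.12 | 16% |
| 20% | 10% | 61.2% | 64.0% | 2.8 | 1.05 | 5% |

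Equal clearing leaves the risk ratio unchanged and costs absolute difference and power. Only unequal clearing moves the ratio.

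**4. Ever reported.** Rescue is offered after a woman reports the symptom, so that report is already counted. The ever/never comparison stays at 68% v 80% with 41% power.

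**5. Cholesterol.** Observed difference = 15.3 − (excess share treated under tamoxifen) × (mg/dL lowering). With SE = 15.3/(1.960 + 0.842) = 5.46 and an assumed lowering of 40 mg/dL:

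| Excess treated | Observed difference (mg/dL) | Power |
|---|---|---|
| 0% | 15.3 | 80% |
| 5% | 13.3 | 68% |
| 10% | 11.3 | 54% |
| 20% | 7.3 | 27% |

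At a 10% excess, a lowering of 30 mg/dL gives 12.3 and one of 60 mg/dL gives 9.3.

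**6. Timing of lipid tests.** Treatment prompted by the baseline test is balanced in expectation by randomization. Treatment prompted by the Day 365 test starts after that value is taken. For treatment prompted by trial tests, the year-1 contrast is therefore not differentially affected. The exposure is mainly at Day 730.

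**The case against.** Analysing all values regardless of rescue is a legitimate treatment-policy approach. That stands, and it is why the observed-value analyses should remain primary. What is missing is a statement that this is the intention and the rescue data needed to interpret the result.

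A reader might infer that the drug's harms are certain to be understated, or that the trial could call 5 mg as tolerable as placebo only because intolerance was treated. The documents do not support either reading:
- Section 3.3 reports that low-dose tamoxifen did not significantly worsen menopausal symptoms. The 68% v 80% comes from the 20 mg dose.
- Ever/never symptom comparisons keep the pre-rescue report. Grade 2-4 toxicities, adherence and voluntary withdrawals are also compared by arm.
- The vaginal products are offered for atrophic symptoms. The 35% v 55% in Section 12.5 is for discharge, so it does not illustrate this rescue.
- No section shows that tamoxifen raises cholesterol or that more tamoxifen women would be treated for it. The 15.3 mg/dL is a detectable difference, not an expected one.

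A reader might also infer that rescue-adjusted values should become the primary analysis. That is a debatable choice of estimand. Carrying a pre-rescue score forward can freeze a passing symptom for up to two years. Carrying a lipid value forward can mean carrying baseline, which imputes no change and hides the rise in question.

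Finally, the primary endpoint is untouched, and the longitudinal symptom model belongs to an exploratory aim that Section 12.5 says was not powered. This limits the weight of the point, but the bother score and the lipids fall under Aim 2.

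**Conclusion.** The point holds in a limited form. The protocol provides treatment for three of the outcomes it measures, and Section 12.4 does not account for it in the six-monthly bother-score model, the longitudinal symptom model or, more weakly, the lipid model. Differences between arms in these analyses may be understated if tamoxifen causes the symptoms.

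The size is unknown. The illustrations in the working rest wholly on assumed distributions, uptake and effects. On those assumptions the bother-score difference shrinks by 7% to 44%, even with equal uptake among severe women. The lipid limb needs two further conditions: a tamoxifen-related rise and an excess of treated women in that arm.

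Separately, the concomitant therapy allowed in Section 7.2 is continued medication for chronic illness and medication for unrelated acute illness. That does not clearly cover the treatments in Sections 11.9 and 11.13, and its recording duty is tied to the same list. These sections must be reconciled.

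**What to change.** In Section 12.4, Aim 2 and Exploratory Aim 2:

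1. Keep the observed-value analyses of bother scores, symptom presence and lipids as primary, and state that they estimate the effect regardless of rescue or lipid-lowering treatment.
2. Add an Aim 2 tolerability outcome: the proportion of women in each arm who start treatment for hot flashes, for vaginal symptoms, or to lower lipids after randomization, compared by Fisher's exact test.
3. Add a sensitivity analysis of the presence/absence and dichotomised outcomes that counts a woman as having the symptom from the date she starts treatment for it.
4. For lipids, add a sensitivity analysis that sets aside or imputes values after lipid-lowering treatment starts, without carrying the earlier value forward.
5. Reconcile Section 7.2 with Sections 11.9 and 11.13, and confirm that the recording duty covers these treatments.

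The cost is SAP wording, programming and a check on data capture. Indication and start date must be recorded with each medication: Section 11.15 also names venlafaxine as the antidepressant of choice during the trial, so the drug name alone does not identify hot-flash rescue. Over-the-counter vaginal products may need an explicit entry. The analysis in item 3 can over-count women whose symptom would have resolved anyway; comparison with the observed-value result shows how much that matters. The primary endpoint and clinical management do not change.
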